1.2 BACKGROUND

Innovative and novel tobacco-derived nicotine products like e-vapor products (EVPs) potentially offer reduced risk alternatives to adult consumers of conventional lit-end cigarettes.^[1] The proven strategies of prevention and cessation can be complemented by making available tobacco products that have demonstrated lower risks than conventional cigarettes. There is overwhelming scientific evidence regarding a risk continuum in the range of tobacco products available currently in the market.

According to this body of evidence, combustible tobacco products like conventional cigarettes are the most risky, and non-combustible tobacco products like EVPs present

Statistical Analysis Plan

relatively lower risks. The Royal College of Physicians' new report, 'Nicotine without smoke: tobacco harm reduction,'^[2] has concluded that EVPs are significantly less risky than cigarettes and likely to be beneficial to public health. E-vapor products deliver nicotine in an aerosol that has a very different composition than a typical aerosol from conventional cigarettes. There are thousands of chemicals generated from the combustion of tobacco, many of which are carcinogenic.^[3, 4] In contrast, far fewer chemicals are generated from heating an e-liquid consisting of carrier ingredients (usually propylene glycol and/or glycerol), nicotine, water, and flavors.^[5] The likely reductions in exposure due to large differences in the chemical composition of aerosols between the cigarettes and EVPs presents harm reduction opportunities for adult smokers switching to EVPs. Nu Mark LLC (Nu Mark) is focused on responsibly developing and marketing innovative tobacco products, such as EVPs, that may reduce the risk of tobacco-related disease.

Altria Client Services LLC (ALCS) and Nu Mark LLC (Nu Mark) are undertaking various studies to evaluate the MarkTen® branded EVPs. These studies will provide scientific evidence to support a Premarket Tobacco Product Application (PMTA) to the Center for Tobacco Products at the Food and Drug Administration (FDA). This specific study will estimate the levels of selected constituents in the exhaled breath of adult EVP users during use of e-vapor products. Data from this study will be used to model potential exposure to non-users when MarkTen® XL e-vapor products are being used. This study is one component of a broader comprehensive framework that will provide the totality of evidence for the PMTA.

1.3 STUDY DESIGN

This is an open-label study designed to estimate the nicotine, glycerin, propylene glycol, menthol, formaldehyde, acetaldehyde, and acrolein levels in exhaled breath samples during use of 4 MarkTen® XL e-vapor products (Table 1). The study design is summarized in Figure 1.

[figure not shown]
[figure not shown]
Statistical Analysis Plan

Table 1. Test Product Summary

Test Product	Test Product Nickname (letter)	Flavor	Percent Nicotine Content, by weight
XL25F	Celine (A)	Fusion	2.5%
XL40B	Rosetta (B)	Bold Classic	4.0%
XL35WM	Monica (C)	Winter Mint	3.5%
XL40B	Spenser (D)	Menthol	4.0%

The study will enroll approximately 32 adult e-vapor-using subjects. Each of the 32 subjects will provide samples for all four test products within the framework of a 4-test product, 4-sequence crossover design. Subjects will make two visits to the site, one screening visit and one visit to provide exhalation samples for four products. Test product sequences will be randomly assigned to subjects at Visit 2 with one test product used per day, for 4 days. Following breath collections, each subject will also use their assigned test product ad libitum for 12 hours each day after the collection of exhaled breath samples. There will be a 10 hour and 55-minute overnight washout period between test product crossovers.

Statistical Analysis Plan

Figure 1. Study Diagram**A. Overall Diagram****B. Daily Test Product Use: Day 1 through Day 4**

Statistical Analysis Plan

1.4 DEFINITION OF THE BASELINE ASSESSMENT

Data collected at the screening visit (e.g., vital signs; Visit 1), will be considered to be baseline values. For primary responses collected from a subject only during Visit 2 the sham concentrations of the each analyte, in a given period, will be considered the baseline (i.e., pre-test product use) concentration of each analyte for that subject, in that period. The sham analyte means will be used to compute test product post-use minus pre-use differences (= sham-corrected amount = SCA) of each of the 7 analyte concentrations of each subject, in each period.

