days). Subjects will complete an exhaled breath test product use session with their assigned test product. An exhaled breath test product use session will consist of the following: one sample with an empty cartridge and inactive battery [sham condition] and one sample using the assigned test product with all exhaled breath collected in one type of trapping container, followed by 45 minutes of rest, then the sham sample and same test product sample collection with a second type of trapping container. Each sample will consist of all the exhaled breath occurring during 10 puffs, each with 5 second puff duration, over 5 minutes (one puff every 30 seconds) collected in the respective sample collection containers:

- Trapping Container 1: captures nicotine, glycerin, propylene glycol, and menthol
- Trapping Container 2: captures formaldehyde, acetaldehyde, and acrolein
- Test product cartridges will be weighed before and after each collection.

Upon completion of the exhaled breath product use session, the subjects will be allowed to use new cartridges with freshly charged “BVR2.3 Rev 05 batteries with topography v2” batteries ad libitum for the next 12 hours following the package insert instructions. These batteries have been verified to perform within acceptance criteria of batteries without topography chip. Cartridges will be weighed before and after use. The “BVR2.3 Rev 05 battery with topography v2” will record all puffs and duration of puff during the 12 hours of ad libitum use. After the 12 hours of ad libitum use, subjects will complete the Use the Product Again Questionnaire.

[figure not shown]
After overnight tobacco and nicotine abstinence, the subjects will have vital signs recorded and repeat the exhaled breath test product use session and 12-hour ad libitum use session with their assigned test product on days 2 through 4 (1 test product per day). After each 12-hour ad libitum use session, subjects will complete the Use the Product Again Questionnaire.

Upon completion of the ad libitum product use session on Day 4, subjects will undergo end-of-study assessments and be released from the site.

[figure not shown]
Overall study time and events are listed in [Table 1](#). Overall design of the study is shown in [Figure 1](#).

Figure 1. Study Diagram

A. Overall Diagram

B. Daily Test Product Use: Day 1 through Day 4

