5.1.2 Visit 2: Day -1 Check-in

Subjects will return to the clinic for their second visit on Day -1, and the following procedures will be completed:

- Review inclusion and exclusion criteria
- Measure vital signs
- Collect urine sample for urine drug and alcohol screening (exhaled breath test for alcohol is also acceptable), urine pregnancy test (all females only)
- Product trial
 1. Subjects will use the products in an assigned order (A, B, C, D)

2. Subject will engage in brief product trial with each e-vapor product (i.e., ad libitum use for 10 minutes).
3. Trials of each e-vapor product will be separated by approximately 30 minutes (from the end of each product trial).
- Review concomitant medications and AEs
- Remind subjects of study restrictions

5.1.3 Visit 2: Day 1 through Day 4

Subjects will abstain from tobacco or nicotine use overnight and repeat the following procedures on Days 1, 2, 3 and 4:

- Measure vital signs
- Subjects will be randomly assigned to a product use schedule (section 5.3)
- Exhaled breath product-use session (1 test product per day for 4 days per randomization schedule)
 1. 10 sham puffs (empty cartridge and inactive battery)
 - 5-second puff duration, one puff every 30 seconds for 5 minutes (Note: All exhaled breath will be captured after the first puff to ~60 seconds after the last puff in Trapping Container 1 with a nose clip in place.) All puff durations will be documented.
 - Subjects will be instructed to inhale as they normally use EVPs and not to only mouth puff.
 - Subjects will also be instructed to make every attempt to exhale directly into the collection device and minimize leakage of the exhaled vapor in the ambient air.
 2. 10 puffs with assigned test product with fully charged standard battery (BVR2.3)
 - 5-second puff duration, one puff every 30 seconds for 5 minutes (Note: All exhaled breath will be captured after the first puff to ~60 seconds after the last puff in Trapping Container 1 with a nose clip in place.) All puff durations will be documented.
 - Subjects will be instructed to inhale the vapor as they normally use EVPs and not to only mouth puff.
 - Subjects will also be instructed to make every attempt to exhale directly into the collection device and minimize leakage of the exhaled vapor in the ambient air.
 3. At least 45 minutes without any tobacco or nicotine use

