4. Cartridge (only test product cartridges) will be weighed within 90 minutes prior to the first 10 puffs. The cartridge will be weighed again after the first exhaled breath measurement and before the second exhaled breath measurement.
5. 10 sham puffs (empty cartridge and inactive battery)
 - 5-second puff duration, one puff every 30 seconds (Note: All exhaled breath will be captured after the first puff to ~60 seconds after the last puff in Trapping Container 2 with a nose clip in place.) All puff durations will be documented.
 - Subjects will be instructed to inhale as they normally use EVPs and not to only mouth puff.
 - Subjects will also be instructed to make every attempt to exhale directly into the collection device and minimize leakage of the exhaled vapor in the ambient air.
6. 10 puffs with the test product
 - 5-second puff duration, one puff every 30 seconds (Note: All exhaled breath will be captured after the first puff to ~60 seconds after the last puff in Trapping Container 2 with a nose clip in place.) All puff durations will be documented.
 - Subjects will be instructed to inhale the vapor as they normally use EVPs and not to only mouth puff.
 - Subjects will also be instructed to make every attempt to exhale directly into the collection device and minimize leakage of the exhaled vapor in the ambient air.
 - Weigh cartridge (test product only) again (within 90 minutes)
- Subject will be allowed to use new cartridges with fully charged (within 24hrs) “BVR2.3 Rev 05 batteries with topography v2” batteries ad libitum for the next 12 hours
- Measure weight of cartridges before and after ad libitum use (within 90 minutes)
- Record all cartridges used with each “BVR2.3 Rev 05 battery with topography v2”. All start and stop times with each cartridge and “BVR2.3 Rev 05 battery with topography v2” will be documented.
- Document likelihood of subject using product again (Use the Product Again Questionnaire) after each 12-hour ad libitum use session
- Review concomitant medications and AEs

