7.0 EVALUATION OF RESPONSE PARAMETERS**7.1 ANALYSIS OF PRIMARY RESPONSE ENDPOINTS**

Sham and test product-derived sample amount of each analyte as well as sham-corrected amount (SCA) of each analyte will be summarized, by test product, per Section 4.1. Sham-corrected analyte amounts will be computed by subtracting corresponding sham response values from test product response values.

Mixed effects ANCOVA models will be fit to separately to the following sham-corrected amount of 7 analytes that will be measured in exhaled breath repeatedly in each subject over the 4 days of Visit 2:

1. Nicotine
2. Glycerin
3. Propylene glycol
4. Menthol
5. Formaldehyde
6. Acetaldehyde
7. Acrolein

The Minimum Detection Limit (MDL) of each analyte is provided in Table 4.

Table 4. Limits of Detection for Exhaled Breath Analytes

Analyte	Nominal MDL (μg)
Propylene glycol	5
Vegetable glycerin	5
Nicotine	0.5
Menthol	0.5
Formaldehyde	0.2
Acetaldehyde	0.2
Acrolein	0.2

Statistical Analysis Plan

Analyte concentrations that are below the Minimum Detection Limit (MDL) will be set to the MDL value for analyses.

Two types of sampling containers were used for collection of the analytes from each subject's exhaled breath (Table 5). Sampling container 1 with one tube and one pad was used for capturing nicotine, glycerin, propylene glycol, and menthol while Sampling container 2 with one tube and 2 pads was used for capturing formaldehyde, acetaldehyde, and acrolein. Exhaled breath samples were collected in 2 independent sampling sessions, separated by 45 minutes, within each period (Figure 1B). Sampling container 1 was used to trap exhaled breath in the first sampling session, while sampling container 2 was used in the second sampling session.

There are two subsamples (1 tube + 1 pad) of each analyte, in each sampling container 1 and three subsamples (1 tube + 2 pads) of each analyte in sampling container 2. Enthalpy Analytical Company will provide data sets with the tube and pad analyte amount from each of the two types of Sample container, for each subject. Pad and tube MDL values of the same analyte will be different from one another. For each sampler, the final amounts for a given analyte will be computed in one of three ways:

1. When both the amounts of analyte in pad(s) and tube are above MDL, the exhaled breath sample (EBS) value will be the sum of the pad and tube values

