2. When the amounts of analyte in pad(s) and tube are both below MDL; EBS value will be the sum of the two MDL values. However, since the MDL is volume dependent, the sum will be considered as below MDL (i.e. <0.5).
3. When the amount of one analyte is MDL, but the other is above MDL. EBS will be the sum of the MDL value and the above BLLOQ value.

Descriptive statistics (number of observations, number of missing, mean, SD, median, minimum, maximum, the first quartile, the third quartile, 95% confidence interval, and coefficient of variation) will be tabulated for each of these analytes by test product. Frequency (n and %) of MDL values will be summarized for each product. If the percentage of MDL values for an analyte is more than 50% in any product group, the analyte will not be analyzed with a mixed model.

Statistical Analysis Plan

Each mixed model will be fit to the data by restricted maximum likelihoods. Covariance structures to account for dependencies among repeated measures, within subjects, will be selected for each model using AIC criteria.^[11] Four candidate covariance structures will be considered: compound symmetry, 1st order autoregressive, 1st order autoregressive with a random subject effect, and unstructured. Each model will include period-specific sham values (as a covariate), sequence, study product, and period as fixed effects; subjects nested within-sequence will be modeled as random effects. Standard residual analyses will be used to examine validity of assumptions for the fixed effect distributions. Response variables will be appropriately transformed (e.g., log, reciprocal, or square root) if the residuals indicate distributional assumptions don't hold. The models will be refit to the transformed data and residual analyses again be performed verify that the transformations corrected the problems.

Mean SCA response with (95% confidence limits), for each test product, will be estimated using SAS Least square means methods in each model. Estimates will be back-transformed to the original scale as necessary. Analyte LSmean estimates (with 95% CIs) for each test product will be tabulated for each model. As an example, the SAS Proc Mixed code to fit the Mixed effects ANCOVA model [with an AR(1) covariance structure] is provided below:

```
ods graphics on;
proc mixed data=evap_data method=REML;
  class seq test_product period subject;
  model Analyte = sham § seq period test_product/residual DDFM=KR;
  Random subject (seq); †

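### The aldehyde sham is taken after active puffing, so SAP 1.4 is wrong to call it a pre-use baseline and SAP 7.1 should not use it as a covariate for the aldehydes

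*SAP*

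**What the plan says.** **Collection order.** Protocol 5.1.3 lists each day's steps: 10 sham puffs and then 10 product puffs into the first container, a pause, then 10 sham puffs and 10 product puffs into the second. The pause is "At least 45 minutes without any tobacco or nicotine use". Protocol 3.1 gives the same order: "followed by 45 minutes of rest, then the sham sample and same test product sample collection with a second type of trapping container". The order is fixed, not randomised; SAP 7.1 states that "Sampling container 1 was used to trap exhaled breath in the first sampling session, while sampling container 2 was used in the second sampling session".

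**Analytes.** Protocol 3.1: "Trapping Container 2: captures formaldehyde, acetaldehyde, and acrolein". Nicotine, glycerin, propylene glycol and menthol go to the first container.

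**Baseline.** SAP 1.4 states that "the sham concentrations of the each analyte, in a given period, will be considered the baseline (i.e., pre-test product use) concentration of each analyte". It describes the sham-corrected amount (SCA) of all seven analytes as an after-use value minus a before-use value.

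**Model.** SAP 7.1 subtracts the sham to form the SCA and uses it again on the right-hand side: "Each model will include period-specific sham values (as a covariate), sequence, study product, and period as fixed effects". It also calls the two daily sampling sessions independent. The model in Protocol 9.5.2 has sequence, product and period as fixed effects and subject within sequence as a random effect. It has no sham covariate.

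**The concern.** The sham for the first container follows overnight abstinence and precedes that day's product. The sham for the second container always follows 10 active puffs of the product under study. One label therefore covers two different quantities, and for the three aldehydes it is the wrong one.

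Two things are at stake. First, the aldehyde results will be used to model exposure of non-users (Protocol 1.3). A reader who trusts SAP 1.4 will take the aldehyde SCA as the change from an abstinent state, when it is the increment from a second set of 10 puffs. Second, a covariate that the product may already have changed is not a baseline. Adjusting for it can move part of a product effect into the covariate, or create a product difference where there is none.

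No aldehyde sample is taken before the first active puffs on any study day, so residue cannot be measured against a true pre-use value.

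**Working it through.** **1. The SAP's own timeline.** SAP 1.3 gives an overnight washout of 10 h 55 min. The nominal session is 5 (sham) + 5 (product) + 45 (rest) + 5 (sham) + 5 (product) = 65 min. Then 24 h − 12 h ad libitum − 65 min = 10 h 55 min, an exact match. The SAP's figure rests on the same order, with the aldehyde sham 45 minutes after active puffing.

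**2. Effect on the SCA by subtraction.** The documents give no residue data, so the following are assumptions: first-order decay with half-life *h*; gap *g* minutes from the sham window to the product window; and *a*, the residue that would be exhaled in one collection window straight after the first 10 active puffs. Protocol 5.1.3 gives the order of the second sham and product samples but no interval. Five minutes of puffing plus a tail of about 60 seconds makes *g* = 5 to 6 if they are back to back.

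- Residue in the sham: a × 2^(−45/h)
- Residue in the product sample: a × 2^(−(45+g)/h)
- Understatement of the SCA: the first minus the second

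With *g* = 5, as a percentage of *a*:

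| h (min) | in sham | in product sample | net |
|---|---|---|---|
| 5 | 0.2 | 0.1 | 0.1 |
| 15 | 12.5 | 9.9 | 2.6 |
| 30 | 35.4 | 31.5 | 3.9 |
| 60 | 59.5 | 56.1 | 3.3 |
| 120 | 77.1 | 74.9 | 2.2 |

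The worst case over all half-lives follows from x = 2^(−g/h) and k = 45/g. The net is x^k × (1 − x), largest at x = k/(k+1). For *g* = 5: 0.9^9 × 0.1 = 3.9%. For *g* = 6: 4.6%. For *g* = 10: 7.4%. For *g* = 15: 0.75^3 × 0.25 = 10.5%. These are shares of the residue *a*, not of the SCA.

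**3. Effect of the covariate.** Let the true increment be 1.00 for all four products. Let the residue in the sham be 0.05 for A and C and 0.15 for B and D (mean 0.10), with 89% of it still present in the product sample (*h* = 30, *g* = 5: 31.5/35.4 = 0.89). All of these are assumptions.

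- Unadjusted mean SCA: 1 − 0.11 × 0.05 = 0.9945 (A, C) and 1 − 0.11 × 0.15 = 0.9835 (B, D).
- Adjusted mean: unadjusted mean − b × (product's sham mean − overall sham mean), where *b* is the slope of SCA on sham.

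| b | A, C | B, D |
|---|---|---|
| none (unadjusted) | 0.99 | 0.98 |
| −0.1 | 0.9945 − 0.005 = 0.99 | 0.9835 + 0.005 = 0.99 |
| −0.5 | 0.9945 − 0.025 = 0.97 | 0.9835 + 0.025 = 1.01 |
| −1 | 0.9945 − 0.05 = 0.94 | 0.9835 + 0.05 = 1.03 |

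A simulation of the 4×4 crossover (32 subjects, fixed subject effects, 200 runs per scenario) agrees: about 0.97 and 1.01 at b = −0.5, and about 0.95 and 1.03 at b = −1. The average over products does not move. At b = −0.5 a spurious difference of 0.011 becomes one of 0.039 in the other direction.

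With a retained share *q*, the spurious difference per unit of residue difference is −(1 − q) unadjusted and −b − (1 − q) adjusted. For negative *b*, adjustment makes it larger when −b exceeds 2(1 − q), which is 0.22 at q = 0.89.

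**The case against.** A reader might infer something stronger: that product carry-over is being subtracted, so the aldehyde results are understated by 5–10% or more. The documents do not support that. Nothing in them shows residual exhaled aldehyde at 45 minutes. Any residue would also be in the product sample that follows the sham, so most of it cancels. A loss of 10% needs a sham residue equal to 10% of the product-derived amount and none of it left a few minutes later.

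The defence has further points that stand:

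- The primary objective is the change from sham to controlled product use. A sham paired closely with its product sample still estimates that, as the increment from those 10 puffs.
- SAP 7.1 sets values below the detection limit to that limit (nominally 0.2 µg for each aldehyde), so a residue that leaves the sham below it changes nothing. An analyte with more than 50% such values in any product group gets no mixed model, and the covariate question then falls away.
- SAP 7.1 already summarises sham and product amounts separately by product.
- The covariate does not always harm. If none of the residue is retained and b = −1, simulated unadjusted means of about 0.95 and 0.85 both become about 0.90, which removes a false product difference.

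What does not stand is the idea that cancellation settles the matter. It applies to the subtraction, not to the covariate. Whether adjustment helps or harms depends on the retained share and the slope; the documents give no value for either.

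**Conclusion.** The baseline definition in SAP 1.4 is wrong for formaldehyde, acetaldehyde and acrolein, in every subject and period. This follows from the documents alone. The description of the sessions as independent is unsupported for these analytes. The sham covariate, which SAP 7.1 adds to the protocol's model, is measured after exposure to the product being compared.

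The numerical effect is conditional. If no residue remains at 45 minutes, there is no bias from carry-over and only the wording is at fault. If some remains, the level of the aldehyde SCA is little affected when the paired samples are close together, within the bounds worked out above. The more serious possibility is distortion of product-specific least-squares means by the covariate. That needs a residue that differs by product; under the assumed values it reached about 2–3 hundredths of the true increment at b = −0.5 and about 5 hundredths at b = −1 relative to the unadjusted means. Half-life, gap, residue size, retained share and slope are all assumptions.

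**What to change.** Keep the collection order and change the text and one model.

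- **SAP 1.4:** state that for the three aldehydes the sham is a value taken at least 45 minutes after product use, and that their SCA is the increment from the second set of 10 puffs. Keep the pre-use wording for the other four analytes.
- **SAP 7.1, sampling:** delete the word independent for the two sessions.
- **SAP 7.1, model:** fit the aldehyde SCA models without the sham covariate, which restores the fixed and random effects of Protocol 9.5.2.
- **SAP 7.1, reporting:** use the planned by-product sham summaries to look for product differences in the aldehyde sham, and show uncorrected product amounts beside the SCA. Equal shams would not exclude a residue common to all products, but such a residue affects the level and not the product comparison.

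Collecting both shams before any product looks attractive, because it would make SAP 1.4 true as written, but it is not recommended. The second product sample would still follow the first 10 active puffs, while its sham would hold no residue. The error becomes a × 2^(−45/h), an overstatement, against the present a × 2^(−45/h) × [1 − 2^(−g/h)], which is always smaller. With *g* = 5 it would rise from 2.6% to 12.5% of *a* at *h* = 15, and from 3.9% to 35.4% at *h* = 30. SAP 7.1 also describes sampling in the past tense, so collection may already have begun.

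The cost is a few sentences and possibly some loss of precision for the aldehydes where sham and product amounts vary in a way the covariate would have absorbed. No new samples or visits are needed.
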